**Table 13: Mortality Rates — ITT Population with Baseline Ordinal Score of 5 or 6, CRP<150 mg/L, and age<85 years**

Analysis Type	Baseline Ordinal Score	Treatment Group	Number of Deaths		Mortality Rate (CI) c			Difference in Mortality Rates at the Specified Time Point d			HR e			P-value f
			n	%	Estimate	80% CI	95% CI	Estimate	80% CI	95% CI	Estimate	80% CI	95% CI	
Time to Death by Day 15														
Primary a	5	Lenzilumab + RDV (N=X)	X	x.x	x.x	x.x, x.x	x.fff	x.x	x.x, x.x	x.x, x.x	x.x	x.x, x.x	x.x, x.x	0.fff
		Placebo + RDV (N=X)	X	x.x	x.xx	x.x, x.x	x.fff							
	6	Lenzilumab + RDV (N=X)	X	x.x	x.x	x.x, x.x	x.fff	x.x	x.x, x.x	x.x, x.x	x.x	x.x, x.x	x.x, x.x	0.fff
		Placebo + RDV (N=X)	X	x.x	x.xx	x.x, x.x	x.fff							
	7	Lenzilumab + RDV (N=X)	X	x.x	x.x	x.x, x.x	x.fff	x.x	x.x, x.x	x.x, x.x	x.x	x.x, x.x	x.x, x.x	0.fff
		Placebo + RDV (N=X)	X	x.x	x.xx	x.x, x.x	x.fff							
	Any BOS	Lenzilumab + RDV (N=X)	X	x.x	x.x	x.x, x.x	x.fff	x.x	x.x, x.x	x.x, x.x	x.x	x.x, x.x	x.x, x.x	0.fff
		Placebo + RDV (N=X)	X	x.x	x.xx	x.x, x.x	x.fff							
Primary with Sensitivity Imputation b	5	Lenzilumab + RDV (N=X)	X	x.x	x.x	x.x, x.x	x.fff	x.x	x.x, x.x	x.x, x.x	x.x	x.x, x.x	x.x, x.x	0.fff
		Placebo + RDV (N=X)	X	x.x	x.xx	x.x, x.x	x.fff							
	6	Lenzilumab + RDV (N=X)	X	x.x	x.x	x.x, x.x	x.fff	x.x	x.x, x.x	x.x, x.x	x.x	x.x, x.x	x.x, x.x	0.fff
		Placebo + RDV (N=X)	X	x.x	x.xx	x.x, x.x	x.fff							
	7	Lenzilumab + RDV (N=X)	X	x.x	x.x	x.x, x.x	x.fff	x.x	x.x, x.x	x.x, x.x	x.x	x.x, x.x	x.x, x.x	0.fff
		Placebo + RDV (N=X)	X	x.x	x.xx	x.x, x.x	x.fff							

Analysis Type	Baseline Ordinal Score	Treatment Group	Number of Deaths		Mortality Rate (CI) c			Difference in Mortality Rates at the Specified Time Point d			HR e			P-value f
			n	%	Estimate	80% CI	95% CI	Estimate	80% CI	95% CI	Estimate	80% CI	95% CI	
	Any BOS	Lenzilumab + RDV (N=X)	X	x.x	x.x	x.x, x.x	x.xxx	x.x	x.x, x.x	x.x, x.x	x.x	x.x, x.x	x.x, x.x	0.xxx
		Placebo + RDV (N=X)	X	x.x	x.xx	x.x, x.x	x.xxx							
Time to Death by Day 29														
Primary a	5	Lenzilumab + RDV (N=X)	X	x.x	x.xx	x.x, x.x	x.xxx	x.x	x.x, x.x	x.x, x.x	x.x	x.x, x.x	x.x, x.x	0.xxx
		Placebo + RDV (N=X)	X	x.x	x.xx	x.x, x.x	x.xxx							
	6	Lenzilumab + RDV (N=X)	X	x.x	x.x	x.x, x.x	x.xxx	x.x	x.x, x.x	x.x, x.x	x.x	x.x, x.x	x.x, x.x	0.xxx
		Placebo + RDV (N=X)	X	x.x	x.xx	x.x, x.x	x.xxx							
	7	Lenzilumab + RDV (N=X)	X	x.x	x.x	x.x, x.x	x.xxx	x.x	x.x, x.x	x.x, x.x	x.x	x.x, x.x	x.x, x.x	0.xxx
		Placebo + RDV (N=X)	X	x.x	x.xx	x.x, x.x	x.xxx							
	Any BOS	Lenzilumab + RDV (N=X)	X	x.x	x.x	x.x, x.x	x.xxx	x.x	x.x, x.x	x.x, x.x	x.x	x.x, x.x	x.x, x.x	0.xxx
		Placebo + RDV (N=X)	X	x.x	x.xx	x.x, x.x	x.xxx							
Primary with Sensitivity Imputation b	5	Lenzilumab + RDV (N=X)	X	x.x	x.xx	x.x, x.x	x.xxx	x.x	x.x, x.x	x.x, x.x	x.x	x.x, x.x	x.x, x.x	0.xxx
		Placebo + RDV (N=X)	X	x.x	x.xx	x.x, x.x	x.xxx							
	6	Lenzilumab + RDV (N=X)	X	x.x	x.x	x.x, x.x	x.xxx	x.x	x.x, x.x	x.x, x.x	x.x	x.x, x.x	x.x, x.x	0.xxx
		Placebo + RDV (N=X)	X	x.x	x.xx	x.x, x.x	x.xxx							
	7	Lenzilumab + RDV (N=X)	X	x.x	x.x	x.x, x.x	x.xxx	x.x	x.x, x.x	x.x, x.x	x.x	x.x, x.x	x.x, x.x	0.xxx

Analysis Type	Baseline Ordinal Score	Treatment Group	Number of Deaths		Mortality Rate (CI) c			Difference in Mortality Rates at the Specified Time Point d			HR e			P-value f
			n	%	Estimate	80% CI	95% CI	Estimate	80% CI	95% CI	Estimate	80% CI	95% CI	
			Placebo + RDV (N=X)	X	x.x	x.xx	x.x, x.x	x.xxx						
Any BOS	Lenzilumab + RDV (N=X)	X	x.x	x.x	x.x	x.x, x.x	x.xxx	x.x	x.x, x.x	x.x, x.x	x.x	x.x, x.x	x.x, x.x	0.xxx
		X	x.x	x.x	x.xx	x.x, x.x	x.xxx							
	Placebo + RDV (N=X)	X	x.x	x.xx	x.x	x.x, x.x	x.xxx							
Time to Death by Day 60														
Primary a	5	Lenzilumab + RDV (N=X)	X	x.x	x.xx	x.x, x.x	x.xxx	x.x	x.x, x.x	x.x, x.x	x.x	x.x, x.x	x.x, x.x	0.xxx
		Placebo + RDV (N=X)	X	x.x	x.xx	x.x, x.x	x.xxx							
	6	Lenzilumab + RDV (N=X)	X	x.x	x.x	x.x, x.x	x.xxx	x.x	x.x, x.x	x.x, x.x	x.x	x.x, x.x	x.x, x.x	0.xxx
		Placebo + RDV (N=X)	X	x.x	x.xx	x.x, x.x	x.xxx							
	7	Lenzilumab + RDV (N=X)	X	x.x	x.x	x.x, x.x	x.xxx	x.x	x.x, x.x	x.x, x.x	x.x	x.x, x.x	x.x, x.x	0.xxx
		Placebo + RDV (N=X)	X	x.x	x.xx	x.x, x.x	x.xxx							
	Any BOS	Lenzilumab + RDV (N=X)	X	x.x	x.x	x.x, x.x	x.xxx	x.x	x.x, x.x	x.x, x.x	x.x	x.x, x.x	x.x, x.x	0.xxx
		Placebo + RDV (N=X)	X	x.x	x.xx	x.x, x.x	x.xxx							
Primary with Sensitivity Imputation b	5	Lenzilumab + RDV (N=X)	X	x.x	x.xx	x.x, x.x	x.xxx	x.x	x.x, x.x	x.x, x.x	x.x	x.x, x.x	x.x, x.x	0.xxx
		Placebo + RDV (N=X)	X	x.x	x.xx	x.x, x.x	x.xxx							
	6	Lenzilumab + RDV (N=X)	X	x.x	x.x	x.x, x.x	x.xxx	x.x	x.x, x.x	x.x, x.x	x.x	x.x, x.x	x.x, x.x	0.xxx
		Placebo + RDV (N=X)	X	x.x	x.xx	x.x, x.x	x.xxx							

Analysis Type	Baseline Ordinal Score	Treatment Group	Number of Deaths		Mortality Rate (CI) c			Difference in Mortality Rates at the Specified Time Point d			HR e			P-value f
			n	%	Estimate	80% CI	95% CI	Estimate	80% CI	95% CI	Estimate	80% CI	95% CI	
7	Lenzilumab + RDV (N=X)	X	x.x	x.x	x.x, x.x	x.XXX	x.x	x.x, x.x	x.x, x.x	x.x	x.x, x.x	x.x, x.x	0.xxx	
		X	x.x	x.xx	x.x, x.x	x.XXX								
	Any BOS	Lenzilumab + RDV (N=X)	X	x.x	x.x	x.x, x.x	x.XXX	x.x	x.x, x.x	x.x	x.x, x.x	x.x, x.x	0.xxx	
		X	x.x	x.xx	x.x, x.x	x.XXX								

CI= Confidence Intervals. N=Number of subjects in the Safety population. n= Number of unique subjects that satisfies the row criteria.

a For the primary endpoint, all subjects whose last assessment was before the corresponding timepoint (Day 15 Visit, Day 29 Visit, Day 60 Visit) and were missing the event were censored at the date of last assessment.

b Primary with Sensitivity Imputation: Same analysis as the initial model but subjects missing event and whose last assessment is before the corresponding timepoint (Day 15 Visit, Day 29 Visit, Day 60 Visit) are non-events for good discharges and censored at Day 15, Day 29, Day 60 respectively or at last assessment for subjects still hospitalized or discharged to LTAC, hospice care, or other hospital.

c Mortality Rates are the Kaplan-Meier estimates.

d Difference in mortality rates (80%, 95% CI) obtained from Kaplan Meier.

e HR is the hazard ratio from the Cox Proportional Hazard Model adjusted for baseline ordinal score and baseline steroid use.

f P-value is based on the Cox adjusted model.

Tables with similar format:

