### 6.4. Covariates and Subgroups

The primary analysis of survival without mechanical ventilation uses baseline ordinal score, baseline CRP, age, and baseline dexamethasone use as covariates in the logistic regression model. This primary analysis will be repeated for the following subgroups: severity of disease, baseline steroid use, baseline use of emerging COVID-19 treatments, duration of symptoms, race, comorbidities (binary 2+ vs less than or equal to 1), age, baseline CRP, and sex. [Table 1](#) provides details of covariates to be used for all analyses of primary, secondary or exploratory endpoints.

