## Appendix 6 BET-B

Endpoint	Analysis	Covariates/Subgroups
Key Secondary Endpoints		
[Note: All key secondary endpoint analyses in the ITT population will be repeated in the mITT population.]		
1. Time to mechanical ventilation or death up to and including Day 29 in subjects who are < 85 years old, have baseline clinical status of 5 or 6, and baseline CRP < 150 mg/L.  [Note: baseline CRP must be available for inclusion in this analysis.]	Primary	
1. Adjust for the following covariates using ITT population:
 
 
Baseline Dexamethasone use
 
Actual baseline ordinal score
 
Baseline CRP (continuous)
 
Age (continuous)
 

	Subgroup	
Repeat the primary analysis for this endpoint within each of the following subgroups using the ITT population:
 
 
Actual baseline ordinal score
 
Baseline use of emerging COVID-19 treatments
 
Duration of symptoms prior to enrollment
 
Race
 
Ethnicity
 
Comorbidities
 
Age (categorical)
 
Sex
 
Baseline CRP (<math>\leq</math> median, <math>></math>median)
 
Baseline CRP (<math><150</math>, <math>\geq 150</math>)
 
 
Baseline dexamethasone use, baseline CRP (continuous), age (continuous), and baseline ordinal score will be included in the subgroup analysis as covariates unless the covariate is the subgroup.

2. Time to Sustained Recovery up to Day 60 in subjects who are < 85 years old, have baseline clinical status of 5 or 6, and baseline CRP < 150 mg/L.	Primary	
1. Adjust for the following covariates using ITT population:
 
 
Baseline Dexamethasone use
 
Actual baseline ordinal score
 
Baseline CRP (continuous)
 
Age (continuous)
 

	Supplementary	
1. Adjust for the following covariates using ITT population:
 
 
Baseline Dexamethasone use
 
Actual baseline ordinal score
 
Age (continuous)
 
Duration of symptoms prior to enrollment (continuous)
 

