## **8.3. Other Secondary Efficacy Analyses**

The analysis described for the other secondary efficacy and safety endpoints in the Master SAP will be followed. However, analysis of secondary endpoints will be conducted for all subjects in the ITT Population and only 95% confidence intervals will be reported for efficacy and safety analyses. For the time to death and mortality endpoints, additional tables for the primary subgroup and full ITT population will be provided in [Table 13](#) and [Table 14](#), respectively. Results for time to death and mortality using subjects with baseline ordinal score of 5 or 6, CRP $\geq$ 150 mg/L, and age $<$ 85 years are provided in [Table 15](#). Results from analysis of time to death using a restricted mean survival approach are provided in [Table 16](#).

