**Table 6: Proportion of Subjects Alive and Without Mechanical Ventilation through Day 29 — mITT Population**

**Table 7: Time to Mechanical Ventilation or Death through Day 29 — ITT Population with Baseline Ordinal Score of 5 or 6, CRP<150 mg/L, and age<85 years**

Analysis/Subgroup	Treatment	Number of Subjects to Mechanical Ventilation or Death d		Median Time Until Event		Hazard Ratio		P-value e			
		n	%	Estimate	95% CI	Estimate	95% CI				
Initial Model a	Lenzilumab + RDV (N=X)	x	x.x	x.x	x.x,x.x	x.x	x.x,x.x	0.xxx			
	Placebo + RDV (N=X)	x	x.x	x.x	x.x,x.x						
Sensitivity b	Lenzilumab + RDV (N=X)	x	x.x	x.x	x.x,x.x	x.x	x.x,x.x	0.xxx			
	Placebo + RDV (N=X)	x	x.x	x.x	x.x,x.x						
Subgroup Analysesc											
Baseline Ordinal Score											
5	Lenzilumab + RDV (N=X)	x	x.x	x.x	x.x,x.x	x.x	x.x,x.x	0.xxx			
	Placebo + RDV (N=X)	x	x.x	x.x	x.x,x.x						
6	Lenzilumab + RDV (N=X)	x	x.x	x.x	x.x,x.x	x.x	x.x,x.x	0.xxx			
	Placebo + RDV (N=X)	x	x.x	x.x	x.x,x.x						
5 or 6	Lenzilumab + RDV (N=X)	x	x.x	x.x	x.x,x.x	x.x	x.x,x.x	0.xxx			
	Placebo + RDV (N=X)	x	x.x	x.x	x.x,x.x						
P-value for interaction e								x.xxx			
Repeat for the rest of the subgroups in Table 1.											
CI=Confidence Intervals.											
N= Number of subjects in ITT Population with Baseline Ordinal Score of 5 or 6, CRP<150 mg/L, and age<85 years. n= Number of unique subjects who progressed to mechanical ventilation or death that satisfies the row criteria.											
a Hazard Ratio (HR) is the hazard ratio calculated from the Cox Proportional Hazard Model comparing Active treatment vs Placebo and adjusting for the baseline dexamethasone use (yes, no), Baseline Ordinal Score (5, 6 or 7), age, and baseline CRP as covariates. All subjects whose last assessment was before Day 29 and were missing the event were censored at the date of last assessment.											
b Same analysis as the initial model but subjects missing event and whose last assessment is before Day 29 are non-events for good discharges and censored at Day 29 or at last assessment for subjects still hospitalized or discharged to LTAC, hospice care, or other hospital.											
c For the subgroup analyses, the model described in a was performed for each level of the subgroup.											
d Number of subjects who progressed to a clinical status of 7 or 8 through Day 29.											

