	Placebo + RDV (N=X)	x	x.x	x.x	x.x,x.x			
	P-value for interaction e							0.xxx
Age								
< 40	Lenzilumab + RDV (N=X)	x	x.x	x.x	x.x,x.x	x.x	x.x,x.x	0.xxx
	Placebo + RDV (N=X)	x	x.x	x.x	x.x,x.x			

Analysis/Subgroup	Treatment	Number of Recovered Subjects		Median Time Until Recovery		Hazard Ratio		P-value e
		n	%	Estimate	95% CI	Estimate	95% CI	
41-64	Lenzilumab + RDV (N=X)	x	x.x	x.x	x.x,x.x	x.x	x.x,x.x	0.xxx
	Placebo + RDV (N=X)	x	x.x	x.x	x.x,x.x			
65 and older	Lenzilumab + RDV (N=X)	x	x.x	x.x	x.x,x.x	x.x	x.x,x.x	0.xxx
	Placebo + RDV (N=X)	x	x.x	x.x	x.x,x.x			
	P-value for interaction e							0.xxx
Sex								
Male	Lenzilumab + RDV (N=X)	x	x.x	x.x	x.x,x.x	x.x	x.x,x.x	0.xxx
	Placebo + RDV (N=X)	x	x.x	x.x	x.x,x.x			
Female	Lenzilumab + RDV (N=X)	x	x.x	x.x	x.x,x.x	x.x	x.x,x.x	0.xxx
	Placebo + RDV (N=X)	x	x.x	x.x	x.x,x.x			
	P-value for interaction e							0.xxx
Baseline CRP								
<= Median	Lenzilumab + RDV (N=X)	x	x.x	x.x	x.x,x.x	x.x	x.x,x.x	0.xxx
	Placebo + RDV (N=X)	x	x.x	x.x	x.x,x.x			
>Median	Lenzilumab + RDV (N=X)	x	x.x	x.x	x.x,x.x	x.x	x.x,x.x	0.xxx
	Placebo + RDV (N=X)	x	x.x	x.x	x.x,x.x			
	P-value for interaction e							0.xxx

CI=Confidence Intervals. N=Number of subjects in the ITT Population with Baseline Ordinal Score of 5 or 6, CRP<150 mg/L, and age<85 years. n= Number of unique recovered subjects that satisfies the row criteria.

a Hazard Ratio (HR) is the hazard ratio calculated from the Cox Proportional Hazard Model comparing Active treatment vs Placebo. All subjects lost to follow-up before recovery are censored at last assessment date.

b Sensitivity Analysis 1: Subjects discharged to a location other than LTAC, hospice care, or other hospital are considered recovered and censored at Day 60. The rest of lost to follow-up subjects are censored at last assessment date. Model a was fit to estimate the HR, 95% CI and p-values.

c Supplemental Analysis 1 (age and duration of symptoms prior to enrollment): In addition to the variable included in the model described in a, age and duration of symptoms prior to enrollment as additional covariates were added to the model when estimating the HR, 95% CI and p-values. Same censoring as in model a.

d For the subgroup analyses, the model described in a was performed for each level of the subgroup.

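### The BET-B mortality Cox model leaves out age and CRP, which the primary and main key secondary models include, and no reason is given; the cost is a modest loss of precision

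*SAP*

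**What the plan says.** SAP Section 8.3 adds BET-B-specific mortality output: "For the time to death and mortality endpoints, additional tables for the primary subgroup and full ITT population will be provided". The shell is Table 13, where footnote e defines the effect measure: "HR is the hazard ratio from the Cox Proportional Hazard Model adjusted for baseline ordinal score and baseline steroid use". Tables 14 (full ITT) and 15 (CRP of 150 mg/L or more) are listed as having the same format, so they inherit the footnote.

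The other main models use a larger set. SAP Section 6.4 says that the primary analysis "uses baseline ordinal score, baseline CRP, age, and baseline dexamethasone use as covariates in the logistic regression model". SAP Table 1 gives the same four covariates for the main model of each key secondary endpoint. The closest comparator is the Cox model for time to ventilation or death, described in Table 7, footnote a, as "adjusting for the baseline dexamethasone use (yes, no), Baseline Ordinal Score (5, 6 or 7), age, and baseline CRP as covariates".

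Two further items bear on the point. SAP Table 1 refers the covariates of other secondary endpoints, which include mortality, to Table 6 of the master SAP, and that document is not available here. The notes to Table 13 also state "N=Number of subjects in the Safety population", although the table title names an ITT subgroup.

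**The concern.** Death is half of the primary composite. Inside the composite it is analysed with adjustment for age and CRP; on its own it is not. Mortality has fewer events than the composite, so precision matters more there. Leaving out a prognostic covariate in a Cox model pulls the hazard ratio toward 1, lowers power, and leaves the estimate open to chance imbalance in that covariate. Age and CRP are already collected, and SAP Section 6.5.1.1 says neither will be missing in the primary subgroup.

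In the single-score rows of Table 13 the ordinal score is constant, so footnote e leaves steroid use as the only adjustment.

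The Safety label is a separate problem. Under SAP Section 6.3 safety analyses follow the treatment actually received and ITT follows the randomized arm, so the printed denominators would not match the title.

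**Working it through.** **1. The plan's own power figures.** The documents give no power or event count for mortality, so the check starts with the primary endpoint. Inputs from SAP Section 5: 400 in the subgroup, odds ratio 2.5, two-sided alpha 0.049. The split of 200 per arm is assumed from the overall 275:275.
- Control 16%: odds 0.16/0.84 = 0.1905; divided by 2.5 = 0.0762; treated rate 0.0762/1.0762 = 7.08%. Two-proportion power is 79.7% (stated 80%).
- Control 21%: treated rate 9.61%. Power is 88.7% (stated 89%).

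Both figures reproduce.

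**2. Expected deaths.** Rates are the LIVE-AIR values in Protocol Section 1.1.
- Subgroup, 6.5% v 13.8%: 200 × (0.065 + 0.138) = 40.6 deaths.
- Full ITT, 9.5% v 13.9%: 275 × (0.095 + 0.139) = 64.4 deaths.

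Schoenfeld power is Φ(ln HR × √d / 2 − 1.96), with the hazard ratio as placebo over active.
- Subgroup, HR 2.2: 0.788 × 6.372 / 2 − 1.96 = 0.55, so 71%.
- Full ITT, HR 1.38: 0.322 × 8.022 / 2 − 1.96 = −0.67, so 25%.

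**3. Effect of the omission.** Cox simulation, 1,500 trials per row, 1:1, two-sided 0.05, marginal mortality fixed at the rates in step 2. Assumptions that are not in the documents: 40% at score 6 with HR 2.5 against score 5; 80% on steroids with no effect; age and CRP hazard ratios per SD as shown. Monte Carlo error is about 1.2 points per figure (√(0.68 × 0.32 / 1500)); each pair uses the same simulated trials.

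| Age, CRP HR per SD | Subgroup power, without → with age and CRP | Full ITT power, without → with |
|---|---|---|
| 1.0, 1.0 | 68.3% → 68.1% | 36.9% → 37.3% |
| 1.3, 1.1 | 67.6% → 68.4% | 33.9% → 34.9% |
| 1.5, 1.2 | 69.3% → 70.4% | 36.0% → 36.3% |
| 2.0, 1.2 | 68.4% → 71.1% | 34.5% → 38.9% |
| 2.0, 1.5 | 67.2% → 70.9% | 35.3% → 38.5% |
| 2.5, 1.5 | 67.2% → 73.7% | 35.7% → 39.7% |

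The ITT figures exceed the 25% of step 2 because the two risks imply ln(0.861)/ln(0.905) = 1.50, not the reported HR of 1.38.

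The gain is about 0 to 6 points in the subgroup (largest difference 6.5) and 0 to 4 in the ITT population (largest 4.4). In the subgroup at age 2.0 and CRP 1.5 the estimated hazard ratio is 2.25 without and 2.35 with the two covariates, and the standard error is 0.346 v 0.349. The loss therefore comes from the shrunken estimate, not from a larger standard error.

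**4. Validity.** With no treatment effect (age 2.0, CRP 1.5) the rejection rate is 4.8% without and 5.1% with age and CRP.

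**5. Events per term.** Five terms (treatment plus four covariates) on 40.6 deaths give 8.1 per term; the present three give 13.5. The primary model's planning rates give 200 × (0.16 + 0.0708) = 46.2 events, or 9.2 per term.

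**The case against.** The strongest reply is that the smaller set may be deliberate. Protocol Section 9 says each endpoint is analysed in the same way across the BET stages, and the SAP sends mortality covariates to master SAP Table 6. If that table specifies ordinal score and steroid use, footnote e follows a platform rule. This cannot be checked, and it stands as a reason to reconcile before editing. Table 13 does look like a shell that was not fully adapted: it has 80% CI columns although the Appendices introduction limits BET-B to 95% CIs, and a score 7 row in a population restricted to scores 5 and 6. That reading is an inference.

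A reader might also infer that every other efficacy model uses age and CRP. The documents do not support this. The supplementary model for key secondary 2 in SAP Table 1 adds "Duration of symptoms prior to enrollment (continuous") and lists no CRP. The restricted-mean analyses and the Kaplan-Meier futility test have no covariates, and the rates in Table 13 itself are unadjusted: "Mortality Rates are the Kaplan-Meier estimates".

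Nor is it shown that power is given up for nothing. Five terms mean fewer events per term, although the primary model accepts nearly the same ratio. SAP Section 6.5.1.1 expects some missing age or CRP in the full ITT population, so a complete-case model would drop subjects. Deaths are sparser by Day 15, in single-score rows and in Table 15. If 75% fall in the subgroup, 400 of 533 to 550 leaves 133 to 150 patients outside it; at an assumed 10% to 25% mortality that is at most about 13 to 38 deaths, before removing score 7, age 85 or over and missing CRP. These objections limit the fix but do not defeat it.

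A further temptation is to argue that steroid use is nearly constant because 93.7% received corticosteroids in LIVE-AIR. That figure is standard-of-care use in another trial, not baseline use in BET-B.

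**Conclusion.** The point holds as one of precision and consistency. The mortality Cox model omits two covariates that the primary model and the main models for all four key secondary endpoints use, and the BET-B SAP gives no reason. The cost is about 0 to 6 points of power in the subgroup and 0 to 4 in the full ITT population, with a slight pull of the hazard ratio toward 1. With weak prognostic effects (age 1.5, CRP 1.2 per SD) the gain is 1.1 and 0.3 points, within simulation error; the upper end needs an age hazard ratio of 2.0 to 2.5 per SD.

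It would be wrong to infer an invalid test or an error-control problem. Type I error is intact, and SAP Section 6.8 places non-key secondary endpoints outside the hierarchy, so no formal claim depends on this power.

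The N label is a plain inconsistency whatever the master SAP says. It affects the displayed N and crude percentages; it does not of itself change the Kaplan-Meier rates or the hazard ratio.

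**What to change.** Before unblinding, add the mortality models to SAP Table 1 and revise footnote e:
- **Any BOS rows of Tables 13 and 14 (Day 29 and Day 60):** adjust for actual baseline ordinal score, baseline dexamethasone use, continuous age and continuous baseline CRP.
- **Missing age or CRP in the full ITT:** extend the overall-mean rule of SAP Section 6.5.1.1, now written for the imputation model, so that no ITT subject is dropped.
- **Sparse cells (Day 15, single-score rows, Table 15):** keep a smaller, stated covariate set.
- **Master SAP Table 6:** compare it with the new text and state the BET-B departure if they differ.
- **N in Tables 13 to 15:** define it as the ITT population or ITT subgroup in each title.

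The cost is text and shell edits with no new data. The downside is fewer events per parameter in the subgroup, about 8 instead of about 13.5.

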**Table 14: Mortality Rates — ITT Population**

**Table 15: Mortality Rates — ITT Population with Baseline Ordinal Score of 5 or 6, CRP≥150 mg/L, and age<85 years**

**Table 16: Time to Death by Treatment Group, Actual Baseline Ordinal Score, and Analysis Population: Restricted Mean Survival Time Analysis**

Analysis Population	Treatment Group	Actual Baseline Ordinal Score	n	Tau a	Restricted Mean Time to Death (Days)		Difference				
					Estimate	95% CI	Estimate	95% CI			
Time to Death through Day 15											
ITT with BOS 5 or 6, CRP<150 mg/L, and age<85 years	Lenzilumab + RDV (N=X)	5	x	x	x.x	x.x, x.x	x.xx	x.xx, x.xx			
	Placebo + RDV (N=X)		x	x	x.x	x.x, x.x					
	Lenzilumab + RDV (N=X)	6	x	x	x.x	x.x, x.x	x.xx	x.xx, x.xx			
	Placebo + RDV (N=X)		x	x	x.x	x.x, x.x					
	Lenzilumab + RDV (N=X)	Any BOS b	x	x	x.x	x.x, x.x	x.xx	x.xx, x.xx			
	Placebo + RDV (N=X)		x	x	x.x	x.x, x.x					
ITT	Lenzilumab + RDV (N=X)	5	x	x	x.x	x.x, x.x	x.xx	x.xx, x.xx			
	Placebo + RDV (N=X)		x	x	x.x	x.x, x.x					
	Lenzilumab + RDV (N=X)	6	x	x	x.x	x.x, x.x	x.xx	x.xx, x.xx			
	Placebo + RDV (N=X)		x	x	x.x	x.x, x.x					
	Lenzilumab + RDV (N=X)	7	x	x	x.x	x.x, x.x	x.xx	x.xx, x.xx			
	Placebo + RDV (N=X)		x	x	x.x	x.x, x.x					
	Lenzilumab + RDV (N=X)	Any BOS b	x	x	x.x	x.x, x.x	x.xx	x.xx, x.xx			
	Placebo + RDV (N=X)		x	x	x.x	x.x, x.x					
Time to Death through Day 29											
Time to Death through Day 60											
N= Number of subjects in the specified treatment group, actual baseline ordinal score, and analysis population. n = Number of subjects who died. Difference is the difference in the restricted mean time to death between active treatment to placebo. a Tau is the truncation time point for the Restricted Mean Survival Time analysis and is equal to the minimum of the largest observed times in each group. b There were X additional subjects with an Actual Baseline Ordinal Score of 4 that are included in the 'Any BOS' summaries.											

**Table 17: Summary Results of Tipping Point Analysis for the Proportion of Subjects Alive and Without Mechanical Ventilation through Day 29 — ITT Population with Baseline Ordinal Score of 5 or 6, CRP<150 mg/L, and age<85 years**

Probability of event among nonresponders in Placebo + RDV	Probability of event among nonresponders in Lenzilumab + RDV					
	1%	5%	10%	15%	20%	40%
1%	xx.x (xx.x, xx.x)	xx.x (xx.x, xx.x)	xx.x (xx.x, xx.x)	xx.x (xx.x, xx.x)	xx.x (xx.x, xx.x)	xx.x (xx.x, xx.x)
5%	xx.x (xx.x, xx.x)	xx.x (xx.x, xx.x)	xx.x (xx.x, xx.x)	xx.x (xx.x, xx.x)	xx.x (xx.x, xx.x)	xx.x (xx.x, xx.x)
10%	xx.x (xx.x, xx.x)	xx.x (xx.x, xx.x)	xx.x (xx.x, xx.x)	xx.x (xx.x, xx.x)	xx.x (xx.x, xx.x)	xx.x (xx.x, xx.x)
15%	xx.x (xx.x, xx.x)	xx.x (xx.x, xx.x)	xx.x (xx.x, xx.x)	xx.x (xx.x, xx.x)	xx.x (xx.x, xx.x)	xx.x (xx.x, xx.x)
20%	xx.x (xx.x, xx.x)	xx.x (xx.x, xx.x)	xx.x (xx.x, xx.x)	xx.x (xx.x, xx.x)	xx.x (xx.x, xx.x)	xx.x (xx.x, xx.x)
40%	xx.x (xx.x, xx.x)	xx.x (xx.x, xx.x)	xx.x (xx.x, xx.x)	xx.x (xx.x, xx.x)	xx.x (xx.x, xx.x)	xx.x (xx.x, xx.x)

Note: Values presented are odds ratios and their corresponding 95% CI calculated from the logistic regression model adjusting for Baseline dexamethasone, Baseline OS, CRP, and age (cont) with Placebo + RDV as the reference treatment arm.

Table with similar format:

**Table 18: Summary Results of Tipping Point Analysis for the Proportion of Subjects Alive and Without Mechanical Ventilation through Day 29 — ITT Population**

